- 15. Which one of the following best describes the pain or discomfort you have experienced during the past week?
 - a) Free of pain and discomfort.
 - b) Occasional pain or discomfort. Discomfort relieved by non-prescription drugs or selfcontrol activity without disruption of normal activities.
 - c) Frequent pain or discomfort. Discomfort relieved by oral medicines with occasional disruption of normal activities
 - d) Frequent pain or discomfort; frequent disruption of normal activities Discomfort required prescription narcotics for relief.
 - e) Severe pain or discomfort. Pain not relieved by drugs and constantly disrupted normal activities.
- 16. Overall, how would you rate your health during the past week?
 - a) Excellent
 - b) Very good
 - c) Good
- 17. How did you complete the questionnaire? Please select the one answer that best describes your situation
 - a) By myself, without any help from anyone else
 - b) By myself, except someone else circled the answers on the questionnaire form for me
 - c) With the help of someone else
 - d) This questionnaire was completed by a family member, without help from the subject or patient
 - e) This questionnaire was completed by a nurse or other health professional, without help from the subject or patient
 - f) This questionnaire was completed by another person, without help from the subject or patient

Self-Complete HUI-3 HUI-2 Question # Attribute Attribute 1 Vision -2 3 → Hearing
 Sensation Δ 5 Speech 6 7 Emotion 8 Pain 9 → Ambulation
→ ✤ Mobility 10 → Dexterity _-11 ➡ Cognition Cognition 12 13 → Self-Care 14 Emotion 15 Pain

The mappings of the self-complete questions to the HUI-3 and HUI-2 attribute levels are as follows:

From the standard HUI 15-item questionnaire data we are able to determine 8 scores (with differing number of variables in the scoring) which are used to calculate an overall utility score for HUI-3 and HUI-2:

- 1. HUI-3 attribute levels (8 variables; calculated from HUI 15-item questionnaire data)
- 2. HUI-3 single-attribute utility scores (8 variables; calculated from the HUI-3 attribute levels)
- 3. HUI-3 comprehensive health state (1 variable; 8-element vector from HUI-3 attribute levels)
- 4. HUI-3 overall multi-attribute utility score (1 variable; calculated from single-attribute utility scores)
- 5. HUI-2 attribute levels (7 variables; calculated from the HUI-3 attribute levels)
- 6. HUI-2 single-attribute utility scores (7 variables; calculated from the HUI-2 attribute levels)

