- 7. HUI-2 comprehensive health state (1 variable; 7-element vector from HUI-3 attribute levels)
- 8. HUI-2 overall multi-attribute utility score (1 variable; calculated from single-attribute utility scores)

The statistical analysis will be completed utilizing the **OVERALL MULTI-ATTRIUBUTE UTILITY SCORES for HUI-3 and HUI-2**.

The HUI-2 and HUI-3 multi-attribute utility score scales are each defined such that the score for dead is set to 0.00. The score for perfect health (defined as the state having all attributes at level 1) is set to 1.00. The HUI-2 multi-attribute utility scale is defined for the interval -0.03 to 1.00; the HUI-3 multi-attribute utility scale is defined for the interval -0.36 to 1.00. Negative scores represent states considered worse than dead.

The following instructions guide the user in the determination of HUI-3 and HUI-2 attribute levels and overall multi-attribute utility scores for each subject:

1. Determining HUI-3 Attribute Levels (8 variables)

The levels are Vision, Hearing, Speech, Emotion, Pain, Ambulation, Dexterity, and Cognition. Four of these attributes (vision, hearing, speech, and cognition) each require input from sets of two questions to determine the attribute level.

The scoring methods for HUI-3 Attribute Levels can be found in Tables 15-19:

Table 15:HUI-3 Vision Attribute Level Decision Table

(based on self-complete questionnaire responses)

	Question #2 Response						
Question #1 Response	a	b	C.	d			
a	1	2	3	3			
b	2	2	3	3			
с	4	4	5	5			
d	6	6	6	6			

Cerevel

(based on self-c	omplete questionna	ire responses)							
	Question #4 Response								
Question #3 Response	a	b	с	d	e				
a	1	1	1	1	1				
b	2	3	3	3	3				
с	4	5	6	6	6				
d	4	5	6	6	6				
e	6	б	б	6	б				

Table 17:HUI-3 Speech Attribute Level Decision Table

	Question #6 Response							
Question #5 Response a b c	a	b	c	d				
a	1	1	1	1				
b	2	3	5	5				
с	4	4	5	5				
d	4	4	5	5				

Table 18:HUI-3 Cognition Attribute Level Decision Table

	Question #12 Response								
Question #11 Response	a	b	с	d	e				
a	1	2	2	5	6				
b	3	4	4	5	6				
С	5	5	5	5	6				
d	6	6	6	6	6				

Table 19: Ambulation, Dexterity, Emotion and Pain Attribute Level Decision Table

(based on self-c	based on self-complete questionnaire responses)										
	Question Response										
Attribute	Question #	a	b	с	d	е	f				
Ambulation	9	1	2	3	4	5	6				
Dexterity	10	1	2	3	4	5	6				
Emotion	7	1	2	3	4	5	n/a				
Pain	8	1	2	3	4	5	n/a				

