The standard, and somewhat arbitrary, HUB attribute levels for comatose study subjects are defined as follows: Vision= Level 6; Hearing= Level 6; Speech= Level 5; Ambulation= Level 6; Dexterity= Level 6; Emotion= Level 3; Cognition= Level 6; and Pain= Level 3.

2. Determining HUI-2 Attribute Levels (7 variables)

The levels are Sensation, Mobility, Cognition, Self-Care, Emotion, Pain, and Fertility. HU1-2 level codes for sensation and mobility attributes are derived directly from previously determined HUI-3 attribute level codes. Note: To distinguish clearly previously determined HUI-3 levels from HUI-2 levels being determined, the HUI-3 levels are printed as words and the HUI-2 levels are specified using numerals.

The scoring methods for HUI-2 Attribute Levels can be found in Tables 20-24:

Table 20: HUI-2 Sensation Attribute Level Decision Table

(based on levels of HUI-3 attributes of vision, hearing, and speech) **HUI-3** Levels **HUI-3** Levels of Speech Vision Hearing One Two Three Four Five One One One Two One Three One Four One Five One Six Two One Two Two Two Three Two Four Two Five Two Six Three or Four or Five One Three or Four or Five Two Three or Four or Five Three Three or Four or Five Four Three or Four or Five Five Three or Four or Five Six Six One Six Two Six Three Six Four Six Five Six Six

Table 21: HUI-2 Mobility Attribute Level Decision Table

HUI-3 Levels of	HUI-3 Levels of Dexterity								
Ambulation	One	Two	Three	Four	Five	Six			
One	1	1	1	1	1	1			
Two	2	2	2	2	2	2			
Three	3	3	3	3	3	3			
Four	3	3	3	3	3	3			
Five	4	4	4	4	4	4			
Six	4	4	4	4	4	5			

cerevel

Question #11	Question #12 Response						
Response	a	b	с	d	e		
a	1	2	2	3	4		
b	2	2	2	3	4		
с	2	3	3	3	4		
d	4	4	4	4	4		

HUI-2 Cognition Attribute Level Decision Table Table 22:

Table 23:	HUI-2 Self-Care, Emotion, and Pain Attributes Level Decision Table
-----------	--

	Question Response								
Attribute	Question #	a	b	с	d	e			
Self-Care	13	1	2	3	4	n/a			
Emotion	14	1	2	3	4	5			
Pain	15	1	2	3	4	5			

HUI-2 Fertility Attributes Level Decision Table Table 24:

The HUI2 fertility attribute level code is assumed to be level 1

The standard, and somewhat arbitrary, HUI-2 attribute levels for comatose study subjects are as follows: Sensation= Level 4; Mobility= Level 5; Emotion= Level 3; Cognition Level 4; Self-Care= Level 4; Pain= Level 3; and Fertility= Level 1.

3. Determining Single-Attribute HUI-3 Utility Scores (8 variables)

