Single-attribute utility functions provide preference scores of relative desirability for functional capacity within single attributes defined by the HUI-3 health status classification system. The HUI-3 levels are labelled using integers. Each single-attribute utility function is defined on a scale from 0.00 to 1.00.

The most disabled level of an attribute has a single-attribute utility score of 0.00, and no disability of an attribute has a single-attribute utility score of 1.00.

Cerevel

Attribute	Vision	Hearing	Speech	Ambulation	Dexterity	Emotion	Cognition	Pain
Level	u_1	u ₂	u ₃	u4	u5	u ₆	u7	u ₈
1	1.00	1.00	1.00	1.00	1.00	1.00	1.00	1.00
2	0.95	0.86	0.82	0.83	0.88	0.91	0.86	0.92
3	0.73	0.71	0.67	0.67	0.73	0.73	0.92	0.77
4	0.59	0.48	0.41	0.36	0.45	0.33	0.70	0.48
5	0.38	0.32	0.00	0.16	0.20	0.00	0.32	0.00
6	0.00	0.00	n/a	0.00	0.00	n/a	0.00	n/a

Scoring is as follows:

Legend: u_x: single-attribute utility function for attribute x, n/a: not applicable

Note: The mean single-attribute utility score for level 3 cognition is greater than the mean single-attribute utility score for level 2 cognition.

4. Determining Single-Attribute HUI-2 Utility Scores (7 variables)

Single-attribute utility functions provide preference scores of relative desirability for functional capacity within single attributes defined by the HUI-2 health status classification system. The HUI-2 levels are labelled using integers. Each single-attribute utility function is defined on a scale from 0.00 to 1.00.

The lack of functional capacity, or most disabled level, in an attribute has a single-attribute utility score of 0.00, and full function, or no disability, for an attribute has a single-attribute utility score of 1.00.

Attribute	Sensation	Mobility	Emotion	Cognition	Self-Care	Pain	Fertility
Level	u_1	u_2	u ₃	u 4	u 5	u ₆	u 7
1	1.00	1.00	1.00	1.00	1.00	1.00	1.00
2	0.87	0.92	0.86	0.86	0.85	0.95	0.75
3	0.65	0.61	0.60	0.66	0.55	0.75	0.00
4	0.00	0.34	0.37	0.00	0.00	0.42	n/a
5	n/a	0.00	0.00	n/a	n/a	0.00	n/a

Scoring is as follows:

Legend: ux: single-attribute utility function for attribute x, n/a: not applicable

5. Determining Overall Health-Related Quality of Life (HRQL) Utility Scores Using HUI-3 Utility Function (1 variable)

To calculate the HUI-3 HRQL Utility Score, the above-determined single-attribute levels are entered into the following health utility formula or subjects who do not have missing data from the 15-item questionnaire:

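### SAP 9.3: the HUI attribute utilities, the overall-score formulas and the stated score minima cannot all be right; as written, scores can fall below the SAP's own ranges

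*SAP*

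**What the plan says.** All of the following is in SAP Section 9.3 unless noted.

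- **Inputs to the overall scores.** In the list of eight scores, item 4 reads "HUI-3 overall multi-attribute utility score (1 variable; calculated from single-attribute utility scores" and item 8 reads "HUI-2 overall multi-attribute utility score (1 variable; calculated from single-attribute utility scores". Step 5 words it differently: "the above-determined single-attribute levels are entered into the following health utility formula". Step 6 uses the same wording for HUI-2.
- **Utility at the worst level.** Step 3 (HUI-3) states: "The most disabled level of an attribute has a single-attribute utility score of 0.00". Step 4 says the same in substance for HUI-2, and both tables show 0.00 at the bottom level of every attribute.
- **Formulas.** Step 5 gives HUI-3 as 1.371 times the product of eight attributes, minus 0.371. Step 6 gives HUI-2 as 1.06 times the product of seven attributes, minus 0.06.
- **Ranges.** "The HUI-2 multi-attribute utility scale is defined for the interval -0.03 to 1.00" and "the HUI-3 multi-attribute utility scale is defined for the interval -0.36 to 1.00". Step 6 repeats −0.03 as the lowest HUI-2 score. Step 5 prints the lowest HUI-3 score as −0.3.
- **Use.** SAP Table 11 (Section 5.11.1) analyses change from baseline to Visit 4 in both overall scores by ANCOVA with baseline score and treatment.

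**The concern.** A product that contains a zero is zero, so one attribute at its worst level reduces each formula to its constant. Those constants lie below the lower limits that the section gives for the same scales. At least one of the three elements (attribute values, constants or minima) must therefore be wrong, and the derivation of a listed endpoint cannot be programmed in a way that satisfies the whole section.

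What is at stake depends on which element is wrong. A mis-stated minimum is cosmetic. Wrong attribute values would distort scores across the scale, not only at the floor. The independent programming in SAP Section 9.7 would not reveal the fault if both programmers work from this specification. The rule also means that any single attribute at its worst level scores the same as all attributes at worst. That is a consequence of the text and not a contradiction of it, but it shows how much weight the zero entries carry.

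**Working it through.** **Inputs.** Attribute utilities from the tables in steps 3 and 4; formulas from steps 5 and 6; ranges from the paragraph on the multi-attribute scales; HUI-2 fertility fixed at level 1 (Table 24). Let p be the product of the attribute utilities.

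**What reproduces.**
- All attributes at level 1: 1.371 × 1 − 0.371 = 1.00 and 1.06 × 1 − 0.06 = 1.00, as stated.
- The tables give 6·6·5·6·6·5·6·5 = 972,000 HUI-3 states and 4·5·5·4·4·5·3 = 24,000 HUI-2 states, the SAP's own counts. The tables therefore appear to have been read correctly.

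**What does not reproduce.**

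| | HUI-3 | HUI-2 |
|---|---|---|
| Floor as written (p = 0) | 1.371 × 0 − 0.371 = −0.371 | 1.06 × 0 − 0.06 = −0.06 |
| Stated minimum | −0.36 | −0.03 |
| Gap | 0.011 | 0.030 |
| Gap as share of stated range | 0.011/1.36 = 0.8% | 0.030/1.03 = 2.9% |
| Smallest p the stated minimum needs | (−0.36 + 0.371)/1.371 = 0.0080 | (−0.03 + 0.06)/1.06 = 0.0283 |

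**Rounding.** Allowing ±0.005 on the stated minima, the smallest p would have to lie between 0.0044 and 0.0117 (HUI-3) or between 0.0236 and 0.0330 (HUI-2). The tables give exactly 0.

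**Integer levels instead of utilities.** One attribute at level 2 and the rest at level 1 gives 1.371 × 2 − 0.371 = 2.371 or 1.06 × 2 − 0.06 = 2.06. Both exceed 1.00, and worse health would score higher. This reading breaks the upper limit instead.

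**Not confined to the all-worst state.**
- One response: question 7 answer e gives HUI-3 emotion level 5 (Table 19), utility 0.00, so U = −0.371 with everything else at level 1. Question 15 answer e gives HUI-2 pain level 5 (Table 23), so U = −0.06.
- The SAP's own comatose states keep emotion and pain at level 3 (HUI-3: "Emotion= Level 3; Cognition= Level 6; and Pain= Level 3"; HUI-2 begins "Sensation= Level 4; Mobility= Level 5; Emotion= Level 3; Cognition Level 4"). They still contain zeros and score −0.371 and −0.06.
- No zeros at all, every attribute one level above worst. HUI-3: 0.38 × 0.32 × 0.41 × 0.16 × 0.20 × 0.33 × 0.32 × 0.48 = 0.000081, U = −0.3709. HUI-2 with fertility at level 1: 0.65 × 0.34 × 0.37 × 0.66 × 0.55 × 0.42 = 0.01247, U = −0.0468. Both are below the stated minima.
- Over all states, 802,186 of 972,000 HUI-3 states (82.5%) fall below −0.36. For HUI-2 with fertility at level 1, 6,290 of 8,000 (78.6%) fall below −0.03. These are shares of possible states, not of expected subjects.

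**Score error, by which element is wrong.**
1. Only the stated minima: none.
2. Only the constants. Assume 1.36/−0.36 and 1.03/−0.03, which with the same utilities reproduce both the minima and 1.00. Then (1.36p − 0.36) − (1.371p − 0.371) = 0.011(1 − p), at most 0.011. Likewise (1.03p − 0.03) − (1.06p − 0.06) = 0.03(1 − p), at most 0.030. Both shrink to 0 at full health.
3. The input values: the error cannot be bounded, because the documents give no other values.

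**The case against.** The strongest case on the other side concerns materiality; the contradiction itself is not in dispute. In the first branch no score changes, because no derivation or model in the SAP uses the stated minima. In the second, the corrected score is a linear transform of the same product. The ANCOVA on change with baseline as covariate would then give identical p-values, and treatment differences would only rescale by 1.36/1.371 = 0.992 and 1.03/1.06 = 0.972. The one exception is a deceased subject, who is assigned 0.00 directly. Only the third branch could alter inference, and the documents do not show that it applies. The endpoint is one of seven other secondary endpoints in a trial that SAP Section 5.4 calls exploratory. Comatose or near-worst states are hardly compatible with inclusion criteria 10 and 11.

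All of this stands as a limit on importance. It does not remove the defect, since a single reachable response takes a score out of range and the reader cannot tell which branch applies.

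Two further points are fair. The −0.3 printed in step 5 may be a text-reading artefact, and nothing here depends on it. The difference between levels and utility scores could be settled by items 4 and 8, but steps 5 and 6 still instruct the programmer otherwise. A reading artefact does not explain HUI-2, where −0.03 appears twice and the 0.00 rule is given in words as well as in the table.

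**Conclusion.** The concern holds. With utilities entered, as items 4 and 8 direct, Section 9.3 yields floors of −0.371 and −0.06 against its own limits of −0.36 and −0.03. Entering levels violates the upper limit instead. The shown contradiction is 0.011 (HUI-3) and 0.030 (HUI-2), and it rests only on figures printed in the SAP. The resulting score error ranges from nil, through those same amounts under the assumed alternative constants, to unbounded if the attribute values are wrong. Which element is wrong, the correct scores and the number of affected subjects cannot be derived from the documents. The reach is one other secondary endpoint; scores can be recomputed from item responses, and the primary and key secondary analyses are untouched. It should be corrected before database lock, mainly because the one branch that could change inference cannot be ruled out from the text.

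**What to change.** Before database lock:

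1. Verify the attribute input values, the formula constants and the stated minima in Section 9.3 (steps 3 to 6, items 4 and 8, and the range paragraph) against the instrument's scoring manual. Correct whichever is wrong so that all three agree.
2. State in steps 5 and 6 exactly what is entered: levels, single-attribute utilities or other values.
3. Give one HUI-3 minimum throughout.
4. Add programming checks that the all-worst state returns the verified minimum, that the all-level-1 state returns 1.00, and that no score lies outside the stated range.

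The cost is one correction to a SAP appendix and a short range check. No new data are needed.

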5.8.2. Primary Estimand

The key research question for the primary endpoint will be addressed with an estimand based on the following attributes:

- 1. Treatments: treatments as randomized regardless of the actual treatment received.
- 2. Target study population of interest: subjects in the modified intent-to-treat (mITT) population.
- 3. Endpoint (variable) of interest: RRatio over the Maintenance Phase.
- 4. Population level summary of interest: difference between CVL-865 treated and placebo subjects in RRatio over the Maintenance Phase.
- 5. Strategy for Intercurrent events (ICEs): a hypothetical strategy will be used to address intercurrent events (ICEs) of potential death, and treatment discontinuations. The data after treatment discontinuations will typically be missing or be treated as missing even if collected. Under the hypothetical strategy, these missing values as the result of ICEs of discontinuation will be assumed to follow the observed trajectory of the subject and thus the endpoint will include only eDiary based response data that occur before discontinuation of treatment. It should be noted that the use of protocol defined rescue medication will not be considered as an ICE.

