PGI-C Score at Visits 2, 3, and 4	mITT	PGI-C score over time will be analyzed using a Mixed Model for Repeated Measures (MMRM) analysis. Treatment group (CVL-865 7.5 mg, CVL-865 25 mg, or placebo), visit, and the interaction between treatment group and visit will be included as fixed factors in the MMRM. Subject will be included as a random effect, and an unstructured covariance structure will be used for the repeated measures. The difference between each CVL-865 level versus placebo at each visit will be estimated based on the LSMeans from the MMRM.
CGI-S Score - Change from Baseline to Visits 2, 3, and 4	mITT	Change from baseline in CGI-S score over time will be analyzed using similar MMRM model as described above for PGI-C score.
CGI-I Score at Visit 2, 3, and 4	mITT	CGI-S score over time will be analyzed using similar MMRM model as described above for PGI-C score.
QOLIE-31 Overall and Domain Score - Change from Baseline to Visit 4	mITT	Changes from baseline in QOLIE-31 Overall Scores will be compared using an ANCOVA model with the baseline score as a covariate and treatment group included in the model as fixed effects in the mITT population. This estimand will include available post-baseline response data that occur before discontinuation of treatment or addition of rescue medication. The differences between each treatment dose group and placebo will be estimated based on the LSMeans difference between each CVL-865 dose group and placebo with corresponding 90% CI. The QOLIE-31 Domain Scores will be analyzed the same way, by each of the following categories: Energy, Emotions, Daily

Endpoint	Analysis Population	Analysis Method
		Activities, Mental Activity, Medication Effects, Seizure Worry, and Overall Quality of Life.
HUI Utility Score - Change from Baseline to Visit 4	mITT	Overall Health-Related Quality of Life (HRQL) Utility Scores (HUI-3 and HUI-2) will be analyzed using an ANCOVA model as described above for QOLIE-31 Overall Scores.

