How much do your seizures bother you? ³	100	75	50	25	0			-	
How much do the above problems and worries about energy distress you overall? ⁹	100%	75%	50%	25%	10%	TOTAL:		÷ 5 =	

			Re	sponse			-	
Scale Question	1	2	3	4	5	6	Subtotal	Final Scale Score (0-100) (Domain Score)
G. Overall Quality of Life Overall, how would you rate your quality of life? (10 = Best Possible Quality of Life; 0 = Worst Possible Quality of Life)	(multip	ly respor	nse by 10)				
How has the quality of life been during the past 4 weeks? ⁸	100	75	50	25	0			
How much does the state of your quality of life distress you overall? ⁹	100%	75%	50%	25%	10%	TOTAL:		÷ 2 =

Note: The total number of items in each scale is listed as the divisor for each subtotal. However, due to missing data, the divisor might actually be less than that as noted. The divisor should be the number of items that the respondent answered within the scale.

¹1=All of the time, 2=Most of the time, 3=A good bit of the time, 4=Some of the time, 5=A little of the time, 6=None of the time

²1=A great deal, 2=A lot, 3=Somewhat, 4=Only a little, 5=Not at all

 $^{3}1$ = Not at all bothersome and 5 = Extremely bothersome

⁴1= Yes, a great deal, 2=Yes, somewhat, 3=Only a little, 4=No, not at all

⁵1=Very worried, 2=Somewhat worried, 3=Not very worried, 4=Not at all worried

⁶1=Very fearful, 2=Somewhat fearful, 3=Not very fearful, 4=Not fearful at all

⁷1=Worry a lot, 2=Occasionally worry, 3=Don't worry at all

⁸1=Very well: could hardly be better, 2=Pretty good, 3=Good and bad parts about equal, 4=Pretty bad, 5=Very bad: could hardly be worse

⁹1=Not at all, 2=Somewhat, 3=Moderately, 4=A lot, 5=Very Much

A QOLIE-31 overall score is obtained using a weighted average of the multi-item scale scores found in the table below (Table 15). If a value for Final Scale Score or Distress Score % is missing, the Weighted Subtotal cannot be calculated. However, if the Distress Score % is available, it can be used for the Sum Distress

QOLIE-31 Scale	Final Scale Score (Domain Score)	Distress Score %		Weighted Subtotal
A. Energy	X		=	
B. Emotions	X		=	
C. Daily Activities	X		=	
D. Mental Activity	X		=	
E. Medication Effects	X		=	
F. Seizure Worry	X		=	
G. Overall QoL	X		=	
	Sum Distress=	: 	Sum Weights=	

Table 14: Formula for Calculating QOLIE-31 Overall Score

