U=1.371(Vison*Hearing*Speech*Ambulation*Dexterity*Emotion*Cognition*Pain)-0.371

HUI-3 allows for negative scores of HRQL that represent health states considered worse than dead. The lowest possible HUI-3 score is -0.3. Note that the overall HRQL utility score for deceased subjects cannot be calculated using the HUB multi-attribute utility function and that this variable should be assigned a score of 0.00. (Dead is an anchor state of the conventional dead=0.00 to perfect health=1.00 overall HRQL utility scale and, therefore, **the score for dead is 0.00** by definition.)

6. Determining Overall Health-Related Quality of Life (HRQL) Utility Scores Using HUI-2 Utility Function (1 variable)

To calculate the HUI-2 HRQL Utility Score, the above-determined single-attribute levels are entered into the following health utility formula **for subjects who do not have missing data from the 15-item questionnaire**:

U=1.06(Sensation*Mobility*Emotion*Cognition*Self-Care*Pain*Fertility)-0.06

HUI-2 allows for negative scores of HRQL that represent health states considered worse than dead. The lowest possible HUI-2 score is -0.03. Note that the overall HRQL utility score for deceased subjects cannot be calculated using the HUB multi-attribute utility function and that this variable should be assigned a score of 0.00. (Dead is an anchor state of the conventional dead=0.00 to perfect health=1.00 overall HRQL utility scale and, therefore, **the score for dead is 0.00** by definition.)

9.4. Columbia-Suicide Severity Rating Scale (C-SSRS) Suicidal Ideation and Suicidal Behavior Scores

The C-SSRS is comprised of 10 categories with binary responses. The 10 categories include:

Category 1 – Wish to be Dead

Category 2 – Non-specific Active Suicidal Thoughts

Category 3 – Active Suicidal Ideation with Any Methods (Not Plan) without Intent to Act

Category 4 – Active Suicidal Ideation with Some Intent to Act, without Specific Plan

Category 5 – Active Suicidal Ideation with Specific Plan and Intent

Category 6 – Preparatory Acts or Behavior

Category 7 – Aborted Attempt

Category 8 – Interrupted Attempt

Category 9 – Actual Attempt (non-fatal)

Category 10 – Completed Suicide

Categories 1-5 represent Suicidal Ideation and categories 6-10 represent Suicidal Behavior. Each category is scored as 1 if there is a positive response in the category and a 0 if there are no positive responses in the category.

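### SAP 9.3 makes both HUI scores depend on all 15 questions, although HUI-3 uses only Q1-Q12 and HUI-2 omits Q7 and Q8, so determined scores are discarded

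*SAP*

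**What the plan says.** The HUI utility score, as change from baseline to Visit 4, is listed among the other secondary efficacy endpoints (SAP section 2, Table 2). The variables analysed are the overall HUI-3 and HUI-2 utility scores (SAP 9.3).

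**Completeness.** Step 5 of SAP 9.3 enters the HUI-3 attribute scores into a "health utility formula or subjects who do not have missing data from the 15-item questionnaire". Step 6 applies the HUI-2 formula "for subjects who do not have missing data from the 15-item questionnaire". The word before 'subjects' differs between the two steps, but the same condition is evidently meant.

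**Items used.** For HUI-3 levels, "Four of these attributes (vision, hearing, speech, and cognition) each require input from sets of two questions to determine the attribute level"; the other four attributes take one question each (Table 19). The HUI-2 levels come from Tables 20-23, with fertility fixed at level 1 (Table 24).

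**Analysis.** Table 11 (SAP 5.11.1) analyses HUI by the ANCOVA described for QOLIE-31 and states no imputation. The QOLIE-31 row says "This estimand will include available post-baseline response data that occur before discontinuation of treatment", and goes on to exclude data after added rescue medication.

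**Death.** In steps 5 and 6, for deceased subjects, "this variable should be assigned a score of 0.00".

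**The concern.** A completeness condition should ask for the inputs a score needs. This one asks for more. A subject who leaves the self-care question (Q13) blank has every HUI-3 attribute level available and still gets no HUI-3 score. A subject who leaves Q7 or Q8 blank has every HUI-2 level available and still gets no HUI-2 score. Change from baseline needs a score before treatment and one at Visit 4, so one such blank at either visit removes the subject from the analysis. Valid data are lost and nothing is gained in return.

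There is also a smaller ambiguity. SAP 9.3 puts a value of 0.00 on the analysed score for a subject who has died, while the data rule that HUI takes from the QOLIE-31 row admits only responses before treatment discontinuation or rescue. A value assigned at death is not such a response. The SAP does not say which text governs, so two programmers could build different datasets.

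**Working it through.** **Step 1. Which questions each index uses (SAP 9.3).**
- HUI-3 formula: "U=1.371(Vison*Hearing*Speech*Ambulation*Dexterity*Emotion*Cognition*Pain)-0.371". Its inputs are vision Q1-Q2 (Table 15), hearing Q3-Q4 (Table 16), speech Q5-Q6 (Table 17), cognition Q11-Q12 (Table 18), and ambulation Q9, dexterity Q10, emotion Q7 and pain Q8 (Table 19). That is 12 questions; Q13, Q14 and Q15 are unused.
- HUI-2: sensation from HUI-3 vision, hearing and speech, so Q1-Q6 (Table 20); mobility from ambulation and dexterity, so Q9-Q10 (Table 21); cognition Q11-Q12 (Table 22); self-care, emotion and pain from Q13, Q14 and Q15 (Table 23). That is 13 questions; Q7 and Q8 are unused.

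**Step 2. Size of the needless loss.** The SAP gives no HUI completion figure to reproduce. Its denominator is 40 evaluable per arm, from 50 × (1 − 0.20) = 40 (SAP 1.2). The blank rate p per item per visit is an assumption, with blanks taken as independent. With k questions required at each of two visits:

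complete pairs = (1 − p)^(2k), with k = 15 as written, 12 for HUI-3, 13 for HUI-2.

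At p = 1%: 0.99^30 = 74.0%, 0.99^24 = 78.6%, 0.99^26 = 77.0%. Subjects recovered per 40: 40 × (0.786 − 0.740) = 1.8 for HUI-3 and 40 × (0.770 − 0.740) = 1.2 for HUI-2.

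| p | all 15 | HUI-3 items | HUI-2 items | HUI-3 recovered per 40 | HUI-2 recovered per 40 |
|---|---|---|---|---|---|
| 0.25% | 92.8% | 94.2% | 93.7% | 0.6 | 0.4 |
| 0.5% | 86.0% | 88.7% | 87.8% | 1.1 | 0.7 |
| 1% | 74.0% | 78.6% | 77.0% | 1.8 | 1.2 |
| 2% | 54.5% | 61.6% | 59.1% | 2.8 | 1.8 |

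**Step 3. Levels fixed by one answer.** In some rows the second question does not matter: Q3 = a gives hearing level 1 for every Q4 answer, and Q5 = a gives speech level 1 for every Q6 answer. For a subject who needs neither Q4 nor Q6, k falls to 10, and at p = 1% complete HUI-3 pairs are 0.99^20 = 81.8%.

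**Step 4. Death, if 9.3 were followed.** Scoring one subject 0.00 in an arm of 40 shifts that arm's mean change by −u/40, where u is the utility the subject would otherwise have had. For assumed u of 0.5 to 0.9 this is −0.0125 to −0.0225.
- Low end: with an assumed SD of change of 0.20, the standard error of the contrast is 0.20 × √(2/40) = 0.0447, and 0.0125/0.0447 = 0.28.
- High end: u = 0.9 with SD 0.10 gives a standard error of 0.10 × √(2/40) = 0.0224 and a ratio of 1.01, but this ignores the variance the outlying value adds. With it, that arm's SD rises from 0.10 to 0.173. Pooling two arms gives √((0.173² + 0.10²)/2) = 0.141, standard error 0.0316, ratio 0.71. Pooling three arms gives √((0.173² + 2 × 0.10²)/3) = 0.129, standard error 0.0288, ratio 0.78.

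The range is therefore about 0.3 to 0.8 standard errors.

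**The case against.** **HUI is a product.** If any attribute is missing, the score is undefined, so strictness is proper. The SAP does let QOLIE-31 domains be averaged over answered items ("The divisor should be the number of items that the respondent answered within the scale"), but averages tolerate gaps that products do not, and the QOLIE-31 overall score also fails when a domain or distress score is missing. This stands against any relaxation for questions an index uses. It does not defend requiring questions the index never uses.

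**Everything rests on an assumed blank rate.** This also stands. The documents do not say whether questions can be skipped. If blanks cluster within subjects, the recoverable number can be smaller, and a wholly skipped questionnaire recovers nothing. A reader might further infer that the rule selects on who skips sensitive questions; the documents offer nothing to support that.

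**The scoring text looks like instrument instructions.** Whether a level may be scored from one answer when its partner is blank depends on sources not available here. That extension is therefore optional below.

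**The death conflict is easily overstated.** A reader might set the 0.00 against SAP 5.8.2, where "a hypothetical strategy will be used to address intercurrent events (ICEs) of potential death, and treatment discontinuations", and call it a contradiction. That strategy is written for the primary endpoint and repeated for the two key secondary seizure endpoints (SAP 5.9.2 and 5.10.1), not for HUI. SAP 9.3 names no visit for the 0.00; Table 8 windows early-termination and unscheduled visits, and a death is neither. The texts can be read together, with 9.3 defining the scale and Table 11 selecting the data, and then no zero enters the ANCOVA. What remains is an ambiguity.

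**Conclusion.** The completeness condition in steps 5 and 6 is wider than either index needs, and this follows from the SAP's own tables without outside information. It can discard determined scores and protects nothing. Under independent blanks of 0.25% to 2% per item per visit, the cost is about 0.6 to 2.8 subjects per 40 for HUI-3 and 0.4 to 1.8 for HUI-2. It is zero if questions cannot be skipped, or if blanks fall only on questions the index needs.

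The death rule needs a clarifying sentence only. One might infer that a single death would dominate an arm; at 0.3 to 0.8 standard errors, and only if a death occurs in an analysed subject and 9.3 is taken to prevail, that is too strong. The utilities and SDs behind this range are assumptions.

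The consequence is limited to an other secondary endpoint in a study the SAP describes as exploratory and without multiplicity adjustment (SAP 5.4). The primary and key secondary results are untouched. The change is worth making because it is nearly free.

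**What to change.** In SAP 9.3, replace the 15-item condition:
- Step 5: HUI-3 is calculated when all eight attribute levels can be determined from Q1-Q12.
- Step 6: HUI-2 is calculated when its six questionnaire-based attribute levels can be determined from Q1-Q6 and Q9-Q15, with fertility fixed at level 1.
- Optional, after checking the instrument's scoring rules: a level counts as determined when the decision table gives the same level for every possible answer to the blank question.

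Add one sentence to 9.3 or to the HUI row of Table 11: the 0.00 for death is not entered in the Table 11 ANCOVA; if a death occurs, a supplementary analysis including it is shown.

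The cost is a few sentences and a small programming change, plus one supplementary table if a death occurs. The decision tables and formulas stay as they are, and every score the present completeness rule keeps is still kept.
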